5.1 Treatment Plan

Phase 1 (Aim 1)

Delivery of Program Sustainability Action Planning Training (intervention protocol).

The Program Sustainability Action Planning Training will be designed to assist states in completing each of the 6 steps in the action planning process and consists of three components (1) pre-workshop preparation, (2) an in-person two day workshop, and (3) ongoing technical assistance and support. Each component will be defined by experiential learning and participation by multiple stakeholders. A sustainability workgroup will be defined for each state consisting of 5-12 members who are actively involved in TC initiatives in the state. To ensure training fidelity, delivery of all training components will be overseen by [name], Principal Investigator and [name], Project Manager.

Preparing for the workshop. Approximately two months before scheduled workshop, we will work with the state tobacco control program manager to identify the list of TC stakeholders who will be involved in workgroup based on our standardized workgroup selection criteria.³¹ Once a list is determined, we will work with the program manager to plan a time to conduct an "Introduction to Sustainability" webinar. This webinar educates listeners on the Program Sustainability Framework (8 domains), defines the parameters one should use when completing PSAT items (i.e., define the "program"), explains how to complete the PSAT online, and provides a time for state-specific Q & A. Prior to the webinar, we will ask the program manager and all stakeholders to complete an *optional* Qualtrics survey, assessing general state tobacco control program sustainability perceptions and individual demographics (age, gender, race, per NIH reporting requirements). Personally identifiable information will not be collected. The pre-

workshop webinar is important for two reasons: (1) it familiarizes all workgroup members with the components of sustainability as outlined in our framework, and (2) introduces the PSAT and steps for completing the PSAT online. The webinar instructs users to answer N/A to PSAT items they are unable to accurately assess. The pre-workshop webinar will last 45 minutes and provide a forum for participants to ask questions about the project. The PSAT will be administered online to all workgroup members and results will be aggregated into a report that will be disseminated to the participants prior to the start of the in person workshop. There will also be follow-up correspondence, discussing state-level results of the PSAT, as well as recommendations for action planning next steps and a summary of resources.

Workshop Day 1. The workshops will take place in each state at the state health department (unless a more convenient site is determined). Trainers will follow an instructor manual and will provide an interactive workbook for completing the main goals for each day. This workbook will prompt users throughout the training to document reactions, ideas, and plans that arise in the workshop. The main goals for Day 1 will include defining the program and reviewing assessment results. Activities for Day 1 will include clarifying the program's mission and vision and specifying the population it currently serves; reviewing the current activities and services that the program is implementing; and clarifying any program and organizational capacities that will be necessary to sustain the activities. PSAT scores will identify sustainability areas that need attention. These goals align with Steps 1-2 of the Program Sustainability Action Planning Model.

Workshop Day 2. The main goal for Day 2 is to develop an action plan. Activities for Day 2 include outlining action plan components including: (1) specific, measureable, attainable, realistic, and time-sensitive (SMART) objectives; (2) specific action steps (activities) for achieving objectives; (3) a timeline for completion of each objective; (4) persons responsible for completing each objective; (5) a clear definition of outcomes and measures for successful completion of each objective and overall plan. The workbook will include activity handouts encouraging discussion around different areas of program sustainability. Handouts will also include templates for action planning and materials for tracking technical assistance interactions. These goals align with Step 3 of the Program Sustainability Action Planning Model.

Technical Assistance and Support. Following the in person two-day workshop, the state TC program will be responsible for executing the action plan and tracking its progress in achieving plan objectives (Steps 4-6 in action planning model). Technical assistance is an essential step in the proposed action planning process and will be focused on building each state program's capacity for quality implementation of the action plan.^{92,93} Technical assistance built on best practice indicators^{17,92-100} will include state-specific quarterly plan review and feedback, assistance in troubleshooting problems with step completion, sharing insights on plan successes from other similar states, and facilitating connections between similarly-focused states. The research team will remain "on call" for states who need assistance beyond the planned quarterly calls. States will also have access to our website <https://sustain tool.org>, which contains a wealth of information on general action plan execution and domain-specific resources to support plan completion and execution. The website is updated quarterly with new resources and materials. States will be encouraged to retake the PSAT at 12 months and repeat the action planning cycle to revise their action plan based on PSAT results and environmental changes, using the indicators and process provided in the original training cycle.

Comparison state protocol

Comparison state programs will participate in the PSAT assessment, record abstraction, and a key informant interview and survey with state program managers at three time points. Before taking the PSAT, we will work with the state tobacco control program manager to identify the list of TC stakeholders who will be involved in workgroup based on our standardized workgroup selection criteria.³¹ Once a list is determined, we will work with the program manager to plan a time to conduct an “Introduction to Sustainability” webinar. This webinar is identical to the webinar issued to the intervention group, because state programs will be informed of their group selection after completing the PSAT. The webinar educates listeners on the Program Sustainability Framework (8 domains), defines the parameters one should use when completing PSAT items (i.e., define the “program”), explains how to complete the PSAT online, and provides a time for state-specific Q & A. Prior to the webinar, we will ask the program manager and all stakeholders to complete an *optional* Qualtrics survey, assessing general state tobacco control program sustainability perceptions and individual demographics (age, gender, race, per NIH reporting requirements). Personally identifiable information will not be collected. The pre-workshop webinar is important for two reasons: (1) it familiarizes all workgroup members with the components of sustainability as outlined in our framework, and (2) introduces the PSAT and steps for completing the PSAT online. The webinar instructs users to answer N/A to PSAT items they are unable to accurately assess. The pre-workshop webinar generally lasts 45 minutes. Comparison states will receive a detailed sustainability assessment report outlining the state’s PSAT scores. There will also be follow-up correspondence, discussing state-level aggregated results of the PSAT, as well as recommendations for action planning next steps. At this point, we will provide a brief packet with resources about program sustainability. However, comparison states will not receive any other component of the training until year four of this project, when they will disseminate the finalized curriculum materials. Some comparison states might independently implement sustainability plans over the course of the grant. We will track implementation and account for it in analyses.

Phase 2 (Aim 2)

(Aim 2): Demonstrate change in sustainability outcomes in states who received the Program Sustainability Action Planning training compared to states who did not.

The overall goal for the Program Sustainability Action Planning Training and subsequent dissemination activities is to increase capacity for sustainability of evidence-based state TC programs through the institutionalization of the program. To determine the extent of reaching this goal, we will design a randomized effectiveness trial to document differences in organizational and programmatic measures and Program Sustainability Assessment Tool scores between intervention and comparison states. We will rely on three sources of data for this study: 1) state-level program records for measures of predictors of sustainability and institutionalization,^{9,11} 2) PSAT scores and 3) a key informant interview and survey with state program managers. While we anticipate that our study will impact behavioral risk factors for tobacco-related diseases (e.g., rates of smoking and initiation), the dependent variable for our study involves measures of program institutionalization and sustainability.

C.6.a. Data collection methods

Pre-Introduction to Sustainability Webinar Survey

All participants will receive an optional Qualtrics survey via email, prior to participating in the “Introduction to Sustainability” webinar. Participants will be asked program sustainability perception questions, as well as demographic questions (age, gender, race, per NIH reporting requirements). Personally identifiable information, such as the participant’s name, will not be collected.

Program Sustainability Assessment Tool (PSAT)

The PSAT has established reliability and face validity for effectively measuring program capacity for sustainability.⁴³ The PSAT contains 40 questions (5 items per 8 domains) and is measured on a 1-7 scale where 1 indicates “To little or no extent” and 7 indicates “To a very great extent”. Users also have the option to choose N/A (Not able to answer), and are encouraged to do so if they are not familiar with that aspect of the program. The PSAT is directly linked to the eight domains outlined in the sustainability framework. Since this framework will be used to guide the action planning for each state, the scores from the PSAT will be important in assessing programmatic challenges and strengths related to sustainability. The sample for our survey is the workgroup defined by the program manager in each of the 24 participating states. We anticipate that 5-12 people in each state will complete the survey. PSAT scores are aggregated across participants for each state so that each state will have an overall PSAT score. Power calculations indicate that surveying workgroups in 24 states (12 intervention, 12 comparison) at three time points- intervention states at baseline and 12 and 24 months post training and comparison states at baseline and 12 and 24 months after baseline collection- will sufficiently capture group differences (Figure 4).

The survey will be conducted online using established methods for Web-based surveys.¹⁰² To enhance the survey response, we will employ the well-established method developed by Dillman.¹⁰³ First, all members of the sample will receive a personalized, advanced notice email. This helps to identify the purpose of the survey and establish its legitimacy. Second, approximately one week after the advance email is sent, all members of the workgroup receive the survey link. In all cases, the replies to the surveys will be anonymous. Third, approximately one week after completion of the PSAT, a follow-up email will be sent to all members of the sample. It will thank those who have already responded and request a response from those who have not yet responded. Finally, once data collection is closed, the workgroup members will receive a detailed sustainability report that includes their responses and an aggregated score for the program. For intervention states, this report will serve in the assessment and planning phases. All correspondence will come from WU and the TCN (an important professional association for our sample). The CDC has also agreed to allow us to participate on the OSH Program Service Branch calls to make CDC program officers aware of their state’s participation and for promotion of our study. We have had previous success with online administration of surveys including the PSAT. Response rate for PSAT administration across the six TC states was 86% (123 out of 143). In another study, in which we administered an email survey among all 50 state TC managers in three waves, with an overall response rate of 97%.^{51,78} In addition, we have years of experience and building partnerships with state TC programs and CDC-OSH.

Program record abstraction

A review and abstraction of state level TC program public records will be performed for all 24 states at three time points- baseline and at the annual CDC progress reporting time (June) in years

2 and 3. This will help in evaluating the impact of the training intervention on the capacity for sustainability and institutionalization of the TC program within the organization.

Step 1: Identifying relevant records and measures. Relevant state-level TC program records will be identified within the 24 selected states from various sources. First, all state tobacco programs are required by CDC (DP15-1509 funding requirements²) to submit an annual progress report. We will begin by using our consultants and empirical literature to identify relevant state-level programmatic measures documented in these annual progress reports. We have also reviewed the DP15-1509 funding requirements for relevance and have outlined the connection between state reporting requirements and established predictors of sustainability and outcomes in Appendix C. This will increase our likelihood of retrieving all relevant information and provide empirical evidence with which to substantiate the responses in the PSAT and identify and address any potential bias therein. In addition, for those metrics not included in the report, we will review state health agency websites and publically available state-level government documentation. [name] has extensive experience in collecting this type of information and has incorporated similar strategies in three other studies.

Step 2: Data abstraction. TC program records will be reviewed and data will be abstracted by two trained evaluators using standardized methods and data collection tools created by the research team. The development and use of a standardized instrument for the review and abstraction will improve inter-rater reliability and will provide quantitative data for monitoring trends and intervention effects.

Step 3: Establishing reliability and validity. Data collected via record review and abstraction are subject to bias that may result from rater subjectivity.¹⁰⁴ In order to determine the agreement between the two evaluators, a baseline reliability evaluation will be conducted early in the process to calculate inter-rater reliability. In order to determine validity of self-reported data from the PSAT, agreement between self-reported and record-based information will be assessed. Both inter-rater reliability and validity of self-reported data will be checked at baseline and two other time points.

Key Informant Interview and Survey

In order to collect additional organizational metrics, a key informant interview and survey will be conducted with state program managers. These will be performed for all 24 states at three time points- baseline and in June during years 2 and 3. This will help in evaluating the impact of the training intervention on the capacity for sustainability and institutionalization of the TC program within the organization.

Step 1: Identifying relevant measures. Relevant state-level sustainability metrics will be identified within the 24 selected states from various sources, including CDC Best Practices, ALA State of Tobacco Control, empirical literature, and consultation of our advisory group.

Step 2: Key Informant Interview and Survey. TC program managers will be contacted to complete a phone interview and survey. The interview and survey will only collect organizational metrics not collected in reporting records, and no personal information will be collected. We will record phone interviews to ensure comprehensive analysis by trained abstracters. Prior to the interview, program managers will be provided a copy of the questions to be asked from a standard script created by the research team. Each question is formatted in multiple choice, e.g., “How long has the program been in existence?” [1: Less than 1 year; 2: 1-3 years; 3: 3-5 years; 4: 5-10 years; 5: 10 or more years; 6: Don’t know]. Using this method, program managers will provide unambiguous answers to data points not collected by record abstraction.

Step 3: Establishing reliability and validity. Data collected via interview/survey and abstraction are subject to bias that may result from rater subjectivity.¹⁰⁴ In order to determine the agreement between the two evaluators, a baseline reliability evaluation will be conducted early in the process to calculate inter-rater reliability. In order to determine validity of self-reported data from the PSAT, agreement between self-reported, record-based information, and interview/survey information will be assessed. Both inter-rater reliability and validity of self-reported data will be checked at baseline and two other time points.

Phase 3 (Aim 3):

C.7. (Aim 3): Actively disseminate The Program Sustainability Action Planning Model and Training Curriculum materials and study results to support future adoption.

[figure not shown]
No treatment with intervention or comparison groups will take place during this phase.

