1. *Develops the first ever evidence-based Program Sustainability Action Planning Model and Training Curriculum.* By establishing an evidence-based method for action planning and technical assistance surrounding program sustainability, we are supporting state TC programs and other evidence-based public health initiatives to sustain their positive impact in a tumultuous funding climate. In addition, this work will advance the field of study of action planning and technical assistance in general which can contribute to aspects of the D&I field beyond sustainability.

2. *Links closely with practice at an opportune time.* As part of the DP15-1509, National State-Based TC Program Funding Announcement set forth by the CDC, all 2015 awarded applicants (includes all states and territories) are “required to develop a sustainability plan to ensure sustainability and maintaining a state based TC program” and “provide measures of execution of all activities as outlined in the sustainability plan.”² Our development of the Program Sustainability Action Planning Training and broad dissemination will assist states in fulfilling this requirement and establishing their capacity to continue sustainability planning over time.

3. Further advances D&I science related to establishing validated measures for sustainability. The study will also provide further clarity on the challenges, benchmarks, and programmatic factors that contribute to sustainability (versus implementation) of an intervention. We will also use the data collected to explore the predictive validity of the Program Sustainability Assessment Tool, which will enable programs to better plan for and improve the sustainability of effective programs.

4. Provides broad dissemination of training materials and results. The curriculum and lessons from the training program will be systematically disseminated (at no cost) to several key audiences (e.g., trainers in federal and state agencies, staff in public health agencies). Since our training program focuses on capacity for sustainability, our methods and approaches will be applicable to numerous other public health issues.

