Data abstraction. State level TC program records will be reviewed and data will be abstracted by two trained evaluators using standardized methods and data collection tools created by the research team. Examples of variables of interest include: implementation of action plan, amount and source of funding allocated for the implementation of tobacco control programs, size of the program and organization, and number of staff dedicated to support programmatic activity. Funding-related information will be collected from annual progress reports of state health departments, annual reports, and funding opportunities of funding agencies relevant to tobacco control. Abstraction will include only records that are publically available and only programmatic and organizational information will be recorded. No individual identifying information will be recorded.

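### Record-based institutionalization measures come first from progress reports that the state programs submit, and nothing in the plan checks whether trained states simply report more fully

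*Combined protocol and SAP*

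**What the plan says.** Section 5.1 (Phase 2, Aim 2) states that "the dependent variable for our study involves measures of program institutionalization and sustainability", and names as one of three data sources "state-level program records for measures of predictors of sustainability and institutionalization".

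Under Program record abstraction, Step 1, CDC requires all state programs "to submit an annual progress report". The team will start there and "identify relevant state-level programmatic measures documented in these annual progress reports". Websites and government documents are consulted for metrics the report lacks. The manager interview gathers only what the records do not hold. The report-based approach is also expected to "provide empirical evidence with which to substantiate the responses in the PSAT and identify and address any potential bias therein".

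The Introduction (Innovation, item 2) describes the CDC requirement that every awardee develop a sustainability plan and supply measures of its execution. It adds that developing the training and its "broad dissemination will assist states in fulfilling this requirement". Workshop Day 2 covers "a clear definition of outcomes and measures for successful completion of each objective and overall plan", and quarterly plan review with feedback follows.

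Section 10.0 (Data abstraction) says: "Examples of variables of interest include: implementation of action plan". The list continues with funding, program and organization size, and staff numbers. For abstracted records, the only threat named is subjectivity of the rater (5.1, Step 3).

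**The concern.** Trained states are taught to set measurable objectives and define outcome measures, and they then receive quarterly feedback on their plan. Those skills could also change what a program writes in its CDC report. If so, a practice equally common in both arms would be found more often in the records of trained states. The difference would arise after baseline and be caused by the intervention itself, so neither randomization nor adjustment for the baseline PSAT would remove it.

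Two conclusions are at stake. The first is the group effect on record-based institutionalization. The second is the validity check on the PSAT. If fuller reporting lifts the records in the same states where PSAT scores rise, the comparison meant to expose PSAT bias would appear to support the scores.

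**Working it through.** **1. The plan's own figure.** Section 9.0 gives an effect size of 1.25 (PSAT change), power 0.80 and α = 0.05, leading to about 9 programs per group. A two-sample t-test calculation gives n = 8.68, rounded up to 9, if one-sided, and n = 11.09, rounded up to 12, if two-sided. The stated 9 matches the one-sided version, which fits Hypothesis 1, and 9 × 4/3 = 12. I therefore use 12 v 12 and a one-sided 5% test. The plan gives no figure for differences in reporting, so steps 3 and 4 are illustrations under stated assumptions.

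**2. The chain, link by link.**

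| Link | Where | Status |
|---|---|---|
| Records are a source for the institutionalization outcome | 5.1, Aim 2 | stated |
| Abstraction starts from the state-submitted report; other sources mainly fill gaps | 5.1, record abstraction Step 1; interview Step 2 | stated |
| Training helps states meet the CDC plan-and-measures requirement | Introduction, Innovation item 2 | stated |
| Workshop and technical assistance go to one arm until year four | 5.1, Comparison state protocol | stated |
| Training changes what the progress report contains | nowhere | inferred |
| Share of outcome items open to this | mapping placed in an Appendix C that is not in the available text | unknown |

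**3. Effect of a pure reporting shift.** Suppose there is no true effect, but reporting alone raises trained states by b standard deviations. With n = 12 per group, the noncentrality is b√(n/2) = b√6 on 22 df, and the false-positive rate is P(T > t₀.₉₅,₂₂).

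| b | 0 | 0.10 | 0.25 | 0.50 | 0.75 | 1.00 |
|---|---|---|---|---|---|---|
| One-sided rate | 5% | 8.0% | 14.7% | 32.4% | 55.4% | 76.7% |

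For fixed b the noncentrality grows with n, so recruiting more states would not help.

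**4. Effect at item level.** Assumptions: 10 yes/no items per state; equal true prevalence in both arms; a state effect with SD 0.5 on the logit scale; and an exposed item that is present being documented with probability 0.90 in trained states and less often in comparison states. Simulated false-positive rates:

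| Items exposed | True prevalence | 90% v 85% | 90% v 80% | 90% v 70% |
|---|---|---|---|---|
| 10 of 10 | 50% | 9% | 16% | 37% |
| 10 of 10 | 70% | 12% | 24% | 59% |
| 3 of 10 | 50% | 6% | 7% | 10% |
| 3 of 10 | 70% | 6-7% | 9% | 14% |

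Equal documentation gives 5%.

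Hand check at prevalence 50% and 90% v 70%, all items exposed:
- Mean difference: 10 × 0.50 × (0.90 − 0.70) = 1.0 item.
- Approximate variance, trained: 10 × 0.45 × 0.55 + (10 × 0.90 × 0.25 × 0.5)² = 2.475 + 1.266 = 3.74.
- Approximate variance, comparison: 10 × 0.35 × 0.65 + (10 × 0.70 × 0.25 × 0.5)² = 2.275 + 0.766 = 3.04.
- SD ≈ √3.39 = 1.84, so b ≈ 0.54. Step 3 puts this somewhat above 32%, in line with 37%.

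With 3 items exposed, the difference is 3 × 0.50 × 0.20 = 0.3. With a similar spread, b ≈ 0.3/1.84 = 0.16, between 8.0% and 14.7%, in line with 10%.

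**5. The planned safeguards.** Two evaluators reading the same report can agree perfectly however complete or incomplete it is. The PSAT-record comparison tests the PSAT and takes the records as the yardstick. The interview is answered by the program manager, so it is not an outside source either. No comparison of reporting completeness between arms is planned.

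**The case against.** A reader might infer that the training is meant to help states complete the progress reports, so that the record outcomes largely measure report writing. The documents do not support this. The requirement named in the Introduction is the sustainability plan and its measures of execution, and the description of the workshop and technical assistance never mentions the report.

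Other points also narrow the concern:

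- The CDC requirement binds all awardees, so comparison states must meet it too. They also receive the same webinar, a PSAT report, recommendations for next steps and a resource packet. The contrast in reporting skill is smaller than trained against untouched.
- Action plan implementation looks the most exposed item, but it is not shown to be an outcome. Section 10.0 defines it as dosage received, and section 9.0 treats it as dose to be controlled for.
- Funding, staff numbers and program size are countable facts, less open to better write-up. Funding data also draw on funding-agency documents.
- The 37-59% figures need every item to be exposed and a 20-point documentation gap, neither of which has a basis in the documents.

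All of this stands, and it limits the claim to a risk of unknown size. It does not supply the missing check: nothing planned would show whether reporting completeness differs by arm.

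**Conclusion.** The concern holds as an unaddressed risk of bias in those record-based measures that depend on how fully a program reports. It is not a demonstrated bias, and it does not extend to all institutionalization outcomes. The step from the training to fuller progress reports is a close inference rather than a stated aim.

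On the assumed figures, the consequence runs from barely above the nominal 5% (about 6%, for 3 exposed items and a 5-point gap) to more than half of null trials (59%, for all items exposed, a 20-point gap and 70% prevalence). Where the trial sits in that range depends on the item list and on actual reporting differences, and the available text settles neither. The remedy is cheap enough to be worth making despite that uncertainty.

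**What to change.** Amend section 5.1 (Program record abstraction, Step 1) and section 10.0 (Data abstraction) as follows.

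1. Tag each abstracted measure by whether its source was written by the program or outside it.
2. Take each measure from the same source type in all 24 states at all three waves. The text does not say whether gaps are filled per metric or per state. If per state, the source itself could differ by arm.
3. Record *not reported* separately from *absent*, and compare its share by arm and wave. Do not automatically treat it as missing in the main analysis: if a practice is mentioned only when present, that would leave nothing but yes values and no information on those items.
4. Prespecify a sensitivity analysis of the group effect, and of the PSAT-record agreement check, limited to measures that the plan already collects from sources the program did not write, such as funding-agency and state government documents. If the effect appears only in program-written measures, qualify the institutionalization conclusion accordingly.

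The cost is a little more abstraction and analysis work. The sensitivity analysis will be imprecise because it rests on fewer measures. Moving the main claim wholly to outside sources would go further, but it would need extra retrieval and would narrow what the PSAT can be checked against. That trade-off is debatable and is not needed here.
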